### **8.1.3. Triplicate Readings**

For 12-lead electrocardiogram (ECG) data only, where triplicate readings are taken, the mean of triplicate readings will replace the separate individual triplicate readings in all calculations.

In case of incomplete triplicate readings (eg, only 2 out of 3 readings were recorded), the mean and/or medians will be calculated, as appropriate, based on the number of readings available.

### **8.1.4. Repeat and Unscheduled Readings**

For vital signs and 12-lead ECG data only, any predose value recorded in addition to the original value or a postdose value recorded within 15 minutes of the original value will be defined as a repeat value; any postdose value recorded more than 15 minutes after the original value will be defined as an unscheduled value. For all other data types (eg, laboratory parameters), any value recorded in addition to the original value will be defined as an unscheduled value.

The original value will be replaced by the last associated repeat value in all calculations.

As unscheduled values are not associated with any scheduled timepoint, they will be excluded from all calculations.

## **8.2. Subject Disposition and Population Assignment**

Subject disposition and population assignment will be listed.

A summary table by treatment will be provided, based on the safety population.

### 8.3. Screening Demographics and Baseline Characteristics

The screening demographics and baseline characteristics including sex, age, race, ethnicity, height, body weight, and body mass index will be listed.

A summary table by treatment will be provided, based on the safety population.

### 8.4. Prior and Concomitant Medication

Prior medication will be defined as medication that ends prior to dosing. Concomitant medication will be defined as medication that starts during or after dosing or starts but does not end prior to dosing.

Prior and concomitant medications will be coded using the World Health Organization Drug Dictionary (WHODrug) Global, Format B3, Version September 2020 (or later if a new version is issued during the study; see the data management plan [DMP] for more details). Prior and concomitant medications will be listed.

### 8.5. Pharmacokinetic Assessments

#### 8.5.1. Pharmacokinetic Analysis

The following PK parameters will be determined where possible from the plasma concentrations of AMG 133 using noncompartmental methods in validated software program Phoenix WinNonlin (Certara, Version 8.1 or higher):

Parameter	Units a	Definition
AUC last	h* $\mu$ g/mL	area under the plasma concentration-time curve from time zero to the time of last quantifiable concentration b
AUC inf	h* $\mu$ g/mL	area under the plasma concentration-time curve from time zero extrapolated to infinity c
%AUC extrap	%	percentage of area under the plasma concentration-time curve due to extrapolation from the last quantifiable concentration to infinity
C max	$\mu$ g/mL	maximum observed plasma concentration
t max	h	time of the maximum observed plasma concentration
t last	h	time of the last quantifiable concentration
t 1/2	h	apparent terminal elimination half-life
CL/F	L/h	apparent total clearance, calculated as Dose/AUC inf
V z/F	L	apparent volume of distribution during the terminal phase, calculated as Dose/(AUC inf * λ z )

a Units are based on concentration units (provided by the bioanalytical lab or preferred units for presentation of PK parameters) and dose units used in the study.

b The area under the concentration-time curve will be calculated using the linear trapezoidal (linear interpolation) rule.

c Based on the last observed quantifiable concentration

Additional PK parameters may be determined where appropriate.

Pharmacokinetic analysis will be carried out where possible using actual dose administered (mg) and actual postdose blood sampling times. If an actual time is missing, the sample concentration result will be treated as missing unless there is scientific justification to include the result using the nominal time.

The parameters  $C_{max}$ ,  $t_{last}$ , and  $t_{max}$  will be obtained directly from the concentration-time profiles. If  $C_{max}$  occurs at more than 1 timepoint,  $t_{max}$  will be assigned to the first occurrence of  $C_{max}$ .

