1.2. Nonclinical Pharmacokinetics

AMG 133 pharmacokinetics (PK) is defined based on intact AMG 133 molecule (anti-GIPR mAb with at least 1 GLP-1 analog peptide) or total AMG 133 (anti-GIPR mAb with or without GLP-1 analog peptide).

The PK of AMG 133 has been evaluated in single-dose studies in the mouse and cynomolgus monkeys with a dose of 5 mg/kg intravenous (IV) and 3 mg/kg subcutaneous (SC), respectively. Exposure of intact and total AMG 133 were also evaluated in the mouse and cynomolgus monkey in repeat-dose toxicology studies including a 4-week exploratory study and a pivotal

Good Laboratory Practices-compliant 13-week SC repeat-dose. The doses evaluated in the 13-week GLP toxicology studies in mice ranged from 25 to 150 mg/kg and in cynomolgus monkeys from 20 to 120 mg/kg. In both the total and intact forms, AMG 133 exhibited linear pharmacokinetics in both mice and cynomolgus monkeys, regardless of the regimens (single or repeat) at all dose levels evaluated. Terminal half-life estimates in the obese cynomolgus monkeys ranged from 231 to 284 hours for total AMG 133, and from 189 to 222 hours for intact AMG 133. Some loss of the GLP-1 moiety of AMG 133 was observed in repeat-dose GLP mouse and cynomolgus monkey toxicology studies, but significant exposure of intact AMG 133 was maintained throughout the study.¹

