Appendix 8: Schedule of Assessments

CONFIDENTIAL Protocol Reference: 20200290

Schedule of Assessments

Activity	Screening	Check-in						Tre	atme	nt Peri	od						EOS/ETa
Study Day	-28 to -2	-1	1	2	3	4 5	6	7	8	15	22	29	43	57	71	92	120
Relative to Dosing (hours)			Predose	24	48	72 9	6 120	0 144	168	336	504	672	1008	1344	1680	2184	2856
In-house Residency		←							→								
Outpatient Visit	X								X	X	X	X	X	X	X	X	X
GENERAL AND SAFETY ASSESSMENTS																	
Informed Consent	X																
Inclusion/Exclusion Criteria Eligibility Review	X	X															
Medical History	X	Xb															
Height, Weight, and BMI	X	Xc															
Drug Screen	X^d	X															
Cotinine Test	X	X															
Adverse Events ^e			+			_											—
Serious Adverse Eventse	+																→
Concomitant Medications ^f	+																
Pregnancy Test (females only)g	X	X															X
Serology	X																
FSH Test ^h	X																
12-lead ECG ⁱ	X	X	X														X
Vital Signs ^j	X	X	X	X	X				X	X	X	X	X	X	X	X	X
Clinical Chemistry, Urinalysis, and Hematologyk	X	X			X				X			X		X		X	X
eGFR ¹	X	X															
Physical Examination ^m	X	X			X							X		X	X	X	X
PHARMACOKINETIC ASSESSMENTS																	
AMG 133 Plasma PK Samples ⁿ			X	X	X	XX	X	X	X	X	X	X	X	X	X	X	X
Anti-AMG 133 Antibody Serum Sample			X							X		X		X			X
INVESTIGATIONAL PRODUCT											·				·		
AMG 133 Dose Administration ^o			X														
Abbreviations: BMI = body mass index: FCG = electron	ocardiooram:	GFD = ect	imated ala	memil	or fi	Iteotic	en ent	e. FOS	- and	of ctue	w FT	= ear	lar torr	ninatio	n:		

Abbreviations: BMI = body mass index; ECG = electrocardiogram; eGFR = estimated glomerular filtration rate; EOS = end of study; ET = early termination; FSH = follicle-stimulating hormone; PK = pharmacokinetic.

a All neutralizing antibody positive subjects and subjects who tested positive for binding ADAs at the final scheduled study visit, defined as the end of study visit, and have clinical sequelae that are considered potentially related to an anti-AMG 133 antibody response will be asked to return for additional follow-up testing until the ADA responses have returned to (1) baseline, (2) a low titer, or (3) the subject has been followed for a period of at least 1 year (± 4 weeks) post-administration of AMG 133.

b Interim medical history only.

^c Weight and BMI only.

^d Alcohol testing is not included at Screening.

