e Adverse events will be recorded from initiation of study treatment on Day 1 until EOS completion. Serious adverse events will be recorded from the time the subject signs the Informed Consent Form until 30 days postdose or EOS visit, whichever is later.

Protocol Reference: 20200290

Labcorp Drug Development Study: 8473020

^fPrior and concomitant medication administration will be recorded beginning at informed consent. In addition, all Investigator-approved medications taken by a subject within 30 days or 5 half-lives (whichever is longer) before Check-in for over-the-counter or prescription medications, and 30 days prior to enrollment for herbal medicines (eg, St. John's wort), vitamins, and supplements, will be recorded on the subject's electronic Case Report Form.

- g Performed in serum at Screening and in urine at all other times for all females. A positive urine pregnancy test will be confirmed with a serum pregnancy test.
- ^h Performed in postmenopausal females only.
- ¹ Electrocardiograms will be collected after the subject has rested in a supine position for at least 5 minutes, and will be obtained prior to the scheduled blood draws.
- ^j Supine blood pressure, supine heart rate, respiratory rate, and oral body temperature will be measured after the subject has been resting in the supine position for at least 5 minutes.
- ^k Clinical chemistry fasted at least 8 hours.
- ¹ eGFR will be calculated using the Modified Renal Disease equation.
- m A full physical examination at Screening and Check-in and a symptom-directed physical examination at other timepoints.
- ⁿ The PK sample collected from predose through 48 hours postdose will have a sampling window of ± 30 minutes, samples collected at outpatient visits will have a sampling window of ± 48 hours. Times of all PK samples will be recorded to the nearest minute.
- Obse administration of AMG 133 is to occur during the morning of Day 1 after an overnight fast of at least 10 hours.

Summary of Amended Protocol Changes

A Phase I, Open-label, Randomized, Parallel-arm, Single-dose Study to Evaluate the Safety, Tolerability, and Pharmacokinetics of AMG 133 Administered Subcutaneously in Healthy Japanese and Caucasian Subjects

Protocol Status: Final Original Protocol Date: 09 August 2021 Protocol Date: 24 August 2021

Investigational Drug: AMG 133

Amgen Protocol Reference Number: 20200290 Labcorp Drug Development Study: 8473020

Study Site:

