### **8.1.1. Handling of Data Quality Issues Due to Coronavirus Disease 2019 and Related Restrictions**

Due to COVID-19 and related restrictions, there is a high risk for impact to data integrity, with the recognized potential for:

- Missed visits, caused by, for example:
  - Subject unable to travel to site due to restrictions, the need to quarantine, or COVID-19 infection
  - Subject unwilling to go to site due to fear of COVID-19 infection
  - Site postponing subject's visit due to investigator not being available (eg, if they have been dispatched to hospital handling COVID19 infections)
- Site unable to replenish supply of investigational product
- Incomplete data entry by sites due to limited resources to support study or no access to source documents or to eCRF
- Outstanding source document verification (SDV) due to sponsor or country restrictions on remote SDV, or no or limited access to site(s) for on-site visits
- Unanswered queries

At the time of the reporting of the study results, all protocol deviations due to COVID-19 or related restriction will be assessed for their severity and impact on the analyses. If needed, appropriate statistical methods will be applied as a mitigating action (eg, data might be categorized into 2 analysis groups, with and without COVID-19 and related restrictions impact); however, this will exclude any imputations of the missing values. Any mitigating actions will be agreed with Amgen Inc. in advance and identified in the CSR.

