#### **8.5.2. Presentation of Pharmacokinetic Data**

If the actual time of sample collection deviates from the nominal time by more than  $\pm 20\%$ , the plasma concentration will be flagged and excluded from the summary statistics.

For plasma concentration data the following rules will apply:

- Values that are BLQ will be set to 0 for the calculation of summary statistics.
- Arithmetic mean or median values that are BLQ will be presented as 0.

For PK parameters the following rule will apply:

- Geometric mean and coefficient of variation will not be calculated for  $t_{last}$  or  $t_{max}$ .

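### The SAP's ±20% time rule is far looser than the protocol's ±48 h window at late visits; separately, the linear trapezoid slightly overstates AUC

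*SAP*

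**What the plan says.** **Time rule.** SAP 8.5.2 says that if the actual sampling time is more than ±20% from nominal, "the plasma concentration will be flagged and excluded from the summary statistics". Protocol Appendix 8, footnote n, says that "samples collected at outpatient visits will have a sampling window of" ±48 hours. The SAP does not mention that window. The outpatient PK times from Day 15 to Day 120 are "336 504 672 1008 1344 1680 2184 2856" hours after dosing. SAP 8.5.3 plans summary tables and mean (+SD) figures of concentration by treatment and time.

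**AUC rule.** SAP 8.5.1, footnote b: "The area under the concentration-time curve will be calculated using the linear trapezoidal (linear interpolation) rule". No log rule is given for the decline. The same section states: "Pharmacokinetic analysis will be carried out where possible using actual dose administered (mg) and actual postdose blood sampling times". AUClast and AUCinf are primary endpoints (SAP 3).

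**Context.** The only half-lives in either document are nonclinical (Protocol 1.2): "Terminal half-life estimates in the obese cynomolgus monkeys ranged from 231 to 284 hours for total AMG 133, and from 189 to 222 hours" for the intact form. Groups have 7 subjects and no hypothesis is tested (SAP 5). SAP 8.1.1 lists "Missed visits, caused by, for example", travel restrictions, quarantine or a visit postponed by the site, among the COVID-19 effects it foresees as possible.

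**The concern.** A percentage tolerance grows with nominal time, but the concentration error from mistiming depends on the absolute delay relative to the half-life. A rule that is strict in the first week therefore becomes very loose by Day 120, where the protocol allows only two days. At stake are the late by-timepoint means and plots, each built from about 7 subjects.

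The AUC rule is a separate matter. A straight line drawn across a log-linear decline lies above the curve, and the late samples are widely spaced. AUClast and AUCinf, and CL/F through AUCinf, would carry the resulting overstatement, and a missed visit on the decline enlarges it.

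**Working it through.** The plan gives no figure on either point, so there is nothing to reproduce.

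**1. Time rule.** Inputs: nominal times and ±48 h from Protocol Appendix 8; ±20% from SAP 8.5.2; half-life (t½) 189 to 284 h from Protocol 1.2, taken as an assumption for humans. Half-width = 0.20 × nominal time. Fold change at the edge = 2^(half-width / t½).

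| Visit | Nominal (h) | ±20% | Accepted range (h) | Fold change at edge, t½ 284 to 189 h |
|---|---|---|---|---|
| Day 15 | 336 | 67 h (2.8 d) | 269–403 | 1.18–1.28 |
| Day 22 | 504 | 101 h (4.2 d) | 403–605 | 1.28–1.45 |
| Day 29 | 672 | 134 h (5.6 d) | 538–806 | 1.39–1.64 |
| Day 43 | 1008 | 202 h (8.4 d) | 806–1210 | 1.64–2.09 |
| Day 57 | 1344 | 269 h (11.2 d) | 1075–1613 | 1.93–2.68 |
| Day 71 | 1680 | 336 h (14.0 d) | 1344–2016 | 2.27–3.43 |
| Day 92 | 2184 | 437 h (18.2 d) | 1747–2621 | 2.90–4.96 |
| Day 120 | 2856 | 571 h (23.8 d) | 2285–3427 | 4.03–8.12 |

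At ±48 h the fold change is 2^(48/284) = 1.12 to 2^(48/189) = 1.19 at any visit on the decline. The protocol window is 48/336 = 14.3% of nominal at Day 15 and 48/2856 = 1.7% at Day 120, so the SAP rule is the looser one at every visit from Day 15. With a longer assumed half-life of 504 h, the Day 120 edge is still 2^(571.2/504) = 2.19 fold.

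One result needs no half-life. Neighbouring ±20% bands overlap whenever the ratio of nominal times is below 1.2/0.8 = 1.5. That holds for Days 22/29 (672/504 = 1.33) and for every neighbouring pair from Day 43 on. The Day 71 band reaches down to 1344 h, which is the Day 57 nominal time. With ±48 h no bands overlap, because the smallest gap is 168 h and 2 × 48 = 96 h.

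Effect on a mean of 7 subjects otherwise alike: one Day 120 sample at the early edge raises the mean by (4.03 − 1)/7 = 43% to (8.12 − 1)/7 = 102%. One at the late edge lowers it by (1 − 1/4.03)/7 = 11% to (1 − 1/8.12)/7 = 13%.

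**2. AUC rule.** From Day 8 to Day 29 the gaps are 168 h, or 168/284 = 0.6 to 168/189 = 0.9 half-lives. After 672 h they are 336, 336, 336, 504 and 672 h, or 336/284 = 1.2 to 672/189 = 3.6 half-lives. Over a mono-exponential interval of x half-lives the linear rule overstates the area by (x·ln2/2)(1 + 2^−x)/(1 − 2^−x) − 1, which is 4.0%, 15.5% and 33.7% at x = 1, 2 and 3. The widest intervals come late and hold little of the area, so the whole-curve error is far smaller.

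Whole-curve model: C(t) proportional to e^(−kt) − e^(−ka·t), with k = ln2/t½ and ka solved from tmax = ln(ka/k)/(ka − k), on the 16 scheduled times, adding Clast/k and comparing with the exact AUCinf. Assumed t½ is 189 to 284 h and assumed tmax 72 to 168 h.

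| Profile | Linear | Linear-up/log-down |
|---|---|---|
| Complete | +1.1 to +2.1% | −0.4 to −1.5% |
| One of Days 22, 29, 43 or 57 missed | about +2 to +5% | −0.4 to −2.0% |
| Days 22 and 29 both missed | +8 to +16% | −0.4 to −3.2% |
| Day 15 missed | +0.2 to +5.9% | down to −4.2% |

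For assumed half-lives of 336 to 672 h, the complete-profile error is +0.5 to +1.4% (linear) against −0.2 to −0.7% (log-down). With Days 22 and 29 both missed it is +1.7 to +6.9% against −0.2 to −1.1%.

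**The case against.** *On the time rule.* A sample 24 days from nominal is already a protocol deviation, and SAP 7 has deviations reviewed before database lock. That stands, but the SAP 7 review serves assignment to populations. Nothing in SAP 8.5.2 removes the single concentration from the means. The Day 120 figure is the extreme edge of one visit. Moreover, 2856 h is 2856/284 = 10 to 2856/189 = 15 of the assumed half-lives, so many true values there may be below quantification; the Day 29 to Day 92 rows may matter more in practice. The overlap of bands shows how loose the tolerance is; it does not mean that a sample is counted twice. A reader might infer that mistimed samples distort the primary AUCs. They do not, because parameters are computed from actual times.

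*On the AUC rule.* Both methods are standard, and on complete profiles the choice is between two small errors of opposite sign. Three stronger readings fail:

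- Not every interval after Day 8 is overstated. With tmax 120 to 168 h the curve is still concave between 168 and 336 h, and the linear rule understates that interval by 0.1 to 2.8%.
- Log-down is not uniformly better. It is worse if Day 15 is missed and tmax is 144 h or later (−4.2% against +0.2% at worst). It is slightly worse at tmax 168 h on complete profiles (t½ 189 and 222 h: −1.45% against +1.23%, −1.22% against +1.19%) and with Day 120 missed (t½ up to about 231 h).
- The documents do not show that the error biases the Japanese–Caucasian comparison. SAP 8.1.1 presents missed visits as a possibility, not as likely, and nothing suggests that they differ by group. With similar half-lives and similar missed visits the error largely cancels. In groups of 7, missed visits could be uneven by chance, but that is conjecture.

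**Conclusion.** The time-rule point stands. The SAP tolerance and the protocol window are not reconciled, and from Day 15 the SAP would keep samples in the concentration summaries that lie well outside the protocol window, by up to 571 h against 48 h at Day 120. The hours and the overlap of bands follow from the documents alone. The 4.0 to 8.1 fold figure rests on monkey half-lives, and at 504 h it would be 2.2 fold. The effect is confined to descriptive means and plots.

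The AUC point stands as a minor one: an overstatement of about 1 to 2% on complete profiles, and of 8 to 16% only if one subject misses both Day 22 and Day 29. It rests on assumed half-lives and tmax, and shrinks if the human half-life is longer. In a descriptive study without hypothesis tests, it does not put the primary endpoints in doubt.

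**What to change.** **SAP 8.5.2:** for outpatient timepoints from Day 15 onward, flag concentrations taken more than ±48 h from nominal and exclude them from the concentration summaries and mean figures. Keep ±20% for in-house samples, including Day 8, where 20% of 168 h is 34 h and so tighter than 48 h. State that excluded values stay in the parameter calculations at their actual times. Cost: one sentence, and a few more late concentrations left out of means and plots.

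**SAP 8.5.1, footnote b:** specify linear-up/log-down trapezoids. Cost: one software setting, a small underestimate near a late peak, and a worse result than the linear rule in the cases named above, chiefly a missed Day 15 sample with a late tmax.

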#### **8.5.1.1. Criteria for the Calculation of Apparent Terminal Elimination Rate Constant and Half-life**

The start of the terminal elimination phase for each subject will be defined by visual inspection and generally will be the first point at which there is no systematic deviation from the log-linear decline in concentrations.

The apparent terminal elimination rate constant ( $\lambda_z$ ) will only be calculated when a reliable estimate can be obtained using at least 3 data points, preferably not including  $C_{max}$ , and the adjusted coefficient for determination of exponential fit ( $R^2$ -adj) of the regression line is  $\geq 0.8$ . Parameters requiring  $\lambda_z$  for their calculation (eg,  $AUC_{inf}$ ,  $t_{1/2}$ ,  $CL/F$ , and  $V_z/F$ ) will only be calculated if the  $R^2$ -adj value of the regression line is  $\geq 0.8$ .

The following regression-related diagnostic PK parameters will be determined, when possible:

Parameter	Units	Definition
$\lambda_z$	1/h	apparent terminal elimination rate constant
$\lambda_z$ Upper	h	end of exponential fit
$\lambda_z$ Lower	h	start of exponential fit
$\lambda_z$ N	NA	number of data points included in the log-linear regression
$\lambda_z$ Span Ratio	NA	time period over which $\lambda_z$ was determined as a ratio of $t_{1/2}$
$R^2$ -adj	NA	adjusted coefficient for determination of exponential fit

Where possible, the span of time used in the determination of  $\lambda_z$  (ie, the difference between  $\lambda_z$  Upper and  $\lambda_z$  Lower) should be  $\geq 2$  half-lives. If the  $\lambda_z$  Span Ratio is  $< 2$ , the robustness of the  $t_{1/2}$  values will be discussed in the CSR.

#### **8.5.1.2. Criteria for Calculation and Reporting of Area Under the Concentration-time Curve**

The minimum requirement for the calculation of  $AUC$  will be the inclusion of at least 3 consecutive concentrations above the lower limit of quantification. If there are only 3 consecutive concentrations, at least 1 should follow  $C_{max}$ .

If the extrapolated area is  $> 20\%$ ,  $AUC_{inf}$  (and derived parameters,  $CL/F$ , and  $V_z/F$ ) may be excluded from the summary statistics and statistical analysis at the discretion of the sponsor or pharmacokineticist.

If  $AUC_{inf}$  cannot be determined reliably for all subjects and/or dose levels, an alternative AUC measure, such as AUC to a fixed timepoint or  $AUC_{last}$ , may be calculated.

#### **8.5.1.3. Criteria for Handling Below the Limit of Quantification or Missing Concentrations for Pharmacokinetic Analysis**

Plasma concentrations below the limit of quantification (BLQ) will be assigned a value of 0 before the first measurable concentration and thereafter BLQ concentrations will be treated as missing. The following rules apply to the specific situations defined below:

- If an entire concentration-time profile is BLQ, it will be excluded from PK analysis.
- Where 2 or more consecutive concentrations are BLQ at the end of a profile, the profile will be deemed to have terminated and any further quantifiable concentrations will be set to missing for the calculation of the PK parameters, unless they are considered to be a true characteristic of the profile of the drug.
- If a predose plasma concentration is missing, it will be set to 0 by default within Phoenix WinNonlin

